3.8.3. Selection of Data in the Event of Multiple Records

Depending on the statistical analysis method, single values may be required for each analysis visit. If multiple valid, nonmissing, continuous measurements exist in one visit, records will be chosen based on the following rules if a single value is needed:

- In general, the baseline value will be the last nonmissing value on or prior to the first dosing date of study drug, unless specified differently. If multiple measurements occur on the same day, the last nonmissing value prior to the time of first dosing of study drug will be considered as the baseline value. If these multiple measurements occur at the same time or the time is not available, the average of these measurements (for continuous data) will be considered the baseline value. For the efficacy endpoints, if no measurements occur prior to the time of first dosing of study drug, the first nonmissing value on the first dosing date of study drug will be considered as the baseline value.
- For postbaseline values:
 - The record closest to the nominal day for that visit will be selected.
 - If there are 2 records that are equidistant from the nominal day, the later record will be selected.
 - If there is more than 1 record on the selected day, the average will be taken, unless otherwise specified.

If multiple valid, non-missing, categorical measurements exist for one visit, records will be chosen based on the following rules if a single value is needed:

- For baseline, the last available record on or prior to the date of the first dose of study drug will be selected. If there are multiple records at the same time or no time recorded on the same day, the value with the lowest severity will be selected unless otherwise specified.
- For postbaseline values:
 - The record closest to the nominal day for that visit will be selected.
 - If there are 2 records that are equidistant from the nominal day, the later record will be selected.
 - If there is more than 1 record on the selected day, the value with the worst severity will be used.

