7.2.1. Summaries of Numeric Laboratory Results

Descriptive statistics will be provided by treatment group for each laboratory test specified in the study protocol as follows:

- Baseline values
- Values at each postbaseline visit
- Change from baseline at each postbaseline visit

A baseline laboratory value will be defined as the last measurement obtained on or prior to the date/time of first dose of study drug. Change from baseline to a postbaseline visit will be defined as the visit value minus the baseline value. The mean, median, Q1, Q3, minimum, and maximum will be displayed to the reported number of digits; SD values will be displayed to the reported number of digits plus 1.

Median (Q1, Q3) of the observed values for the laboratory tests will be plotted using a line plot by treatment group and visit.

In the case of multiple values in an analysis visit, data will be selected for analysis as described in Section 3.8.3.

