7.3. Body Weight and Vital Signs

Descriptive statistics will be provided by treatment group for body weight and vital signs as follows:

- Baseline value
- Values at each postbaseline time point
- Change from baseline at each postbaseline time point

Median (Q1, Q3) of the observed values for vital signs will be plotted by treatment group and visit.

A baseline value will be defined as the last available value collected on or prior to the date/time of first dose of study drug. Change from baseline to a post-baseline visit will be defined as the post-baseline value minus the baseline value.

In the case of multiple values at a visit assessment, data will be selected for analysis as described in Section 3.8.3. No inferential statistics will be generated.

A by-subject listing of vital signs will be provided by subject ID number and visit in chronological order. Body weight will be included in the vital signs listing, if space permits. If not, they will be provided separately.

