7.5. Electrocardiogram Assessment

Number and percent of subjects with new ECG abnormalities at postbaseline visits including those assessments obtained for the purpose of standard of care will be summarize by treatments. Only subjects with baseline ECG assessments will be included in this analysis.

A shift table of the central assessment of ECG results at postbaseline visit including those assessments obtained for the purpose of standard of care compared with baseline values will be presented by treatment group using the following categories: normal, no new abnormality, new abnormality, or missing. The number and percentage of subjects in each cross-classification group of the shift table will be presented. Subjects with a missing value at baseline or postbaseline will not be included in the denominator for percentage calculation. No formal statistical testing is planned.

A by-subject listing for ECG central assessment and ECG abnormalities, including those not required by the protocol (ie. standard of care), will be provided by subject ID number and time point in chronological order.

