	Visit 1: Screening (Day -2 to -1)	Visit 2: Baseline Assessments, Randomization, and Treatment Assessments (Day 1)	Visit 3: Day 3 ^p (±24 hours)	Visit 4: Day 5 (±24 hours)	Visit 5: Day 7 (±24 hours)	Visit 6: Day 9 (±24 hours)	Visit 7: Day 13 (±24 hours)	Visit 8: Day 17 (±24 hours)	Visit 9: Day 22 (±24 hours)	Visit 10: End of study/Day 28 (+3 days)		Optional Extended Viral Monitoring ^k			
												Visit 11: Day 35 (±48 hours)	Visit 12: Day 42 (±48 hours)	Visit 13: Day 49 (±48 hours)	Visit 14: Day 56 (±48 hours)
Concomitant Medications	X	X	X ^m	X	X ^m	X	X	X	X	X					

- a Chest X-ray obtained < 48 hours prior to Screening may be used
- b Existing values collected \leq 6 days prior to Screening may be used
- c Required for women unable to confirm menopause, hysterectomy and/or bilateral oophorectomy
- d On room air
- e Central laboratory testing: hematology and serum chemistry to include WBC with differential, Hgb, platelets, BUN, creatinine, serum albumin, AST, ALT, ALP, and total bilirubin
- f 2 samples total, 1 from each nostril – collected prior to dosing on dosing days
- g PK samples collected for all subjects 4 hours (\pm 30 mins) post-dose Day 1; pre-dose on Days 5, 9, 13, and 17; and anytime on Day 22
- h For hospitalized subjects only: blood will be drawn for serum creatinine at 4 hours (\pm 30 mins) post-dose at Visit 2 (Day 1) and at any time on Days 2, 3 and 4 (approximately 24, 48 and 72 hours post-first presatovir dose if they remain hospitalized at those times).
- i For hospitalized subjects only: PK sample collected at Visit 3 (48 hours [\pm 3 hours] post-first presatovir dose)
- j Only for subjects who agree to the Optional Extended Viral Monitoring at the time of consent
- k Only for subjects who agree to the Optional Extended Viral Monitoring at the time of consent and test positive (or inconclusive) for RSV at Visit 9 (Day 22)
- l Assessment of procedure-related AEs only, if home visit.
- m Not required if home visit.
- n Local troponin testing will be done pre-dose in accordance with the standard assay available and used at the site. Point-of-care “rapid” troponin tests are not acceptable for protocol-mandated troponin testing.
- o If only the upper or lower respiratory tract was assessed prior to consent, a separate local RSV test in the tract not previously assessed must be performed. Subjects who were not tested for RSV as standard of care may consent to the study and be tested for RSV during the Screening visit.

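### The categorical baseline rule in SAP 3.8.3 stops at the date of first dose rather than its time, so a Day 1 post-dose ECG or troponin can become the baseline

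*SAP*

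**What the plan says.** SAP 3.8.3 gives separate baseline rules for continuous and categorical data when a visit has several records.

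- **Continuous.** Same-day repeats are limited by clock time: "the last nonmissing value prior to the time of first dosing of study drug will be considered as the baseline value".
- **Categorical.** The limit is the calendar date: "For baseline, the last available record on or prior to the date of the first dose of study drug will be selected". A tie rule follows: "If there are multiple records at the same time or no time recorded on the same day, the value with the lowest severity will be" the one used. It covers only simultaneous or untimed records.

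Two safety sections set their own baseline, both by date and time. For numeric laboratory results (7.2.1): "A baseline laboratory value will be defined as the last measurement obtained on or prior to the date/time of first dose of study drug". For weight and vital signs (7.3): "A baseline value will be defined as the last available value collected on or prior to the date/time of first dose of study drug".

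The ECG and troponin shift tables (7.5 and 7.6) use categories and define no baseline. For new ECG abnormalities, 7.5 adds: "Only subjects with baseline ECG assessments will be included in this analysis". On timing, a footnote to the Appendix 1 schedule says of troponin: "Local troponin testing will be done pre-dose in accordance with the standard assay available and used at the site". The 12-lead ECG row has no such footnote.

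**The concern.** A baseline should precede exposure. For categorical data the rule does not ensure this on Day 1, because any record from that date qualifies and the last one is taken. ECG and troponin depend on this rule, and they are the two cardiac safety measures in a plan that also pre-specifies cardiac adverse events of interest (7.1.7 and Appendix 2). If an on-drug record becomes the baseline, the subject lands in the wrong cell of the shift table and, for ECG, may be miscounted among subjects with new abnormalities.

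**Working it through.** The SAP states no figure on this point, so the check compares the rules and applies them to assumed subjects.

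**Step 1: which rule reaches which data.**

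| Data | Section | Limit for a Day 1 baseline |
|---|---|---|
| Continuous, same-day repeats | 3.8.3 | time of first dose |
| Numeric laboratory | 7.2.1 | date/time of first dose |
| Weight, vital signs | 7.3 | date/time of first dose |
| Categorical | 3.8.3 | date of first dose only |
| ECG categories | 7.5 | none stated, so 3.8.3 categorical |
| Troponin normal/abnormal | 7.6 | none stated, so 3.8.3 categorical |

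The continuous rule has one exception, which lets a Day 1 value serve when nothing pre-dose exists. It is confined to efficacy endpoints and does not bear on ECG or troponin.

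**Step 2: apply the rules.** Assume both Day 1 records are timed and filed under the Day 1 visit, and that a later visit is abnormal.

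| Assumed subject | Day 1 pre-dose | Day 1 post-dose | Later visit | Cell under the current rule | Cell if limited by time |
|---|---|---|---|---|---|
| A | normal | abnormal | abnormal | abnormal to abnormal | normal to abnormal |
| B | abnormal | normal | abnormal | normal to abnormal | abnormal to abnormal |

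Subject A loses a real on-drug shift. Subject B gains a false one. The tie rule helps neither, because their records carry different times.

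**Step 3: what must be true for this to happen.** There must be more than one Day 1 record, each with a time, and the last must be post-dose and filed under the Day 1 visit.

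- *ECG.* Appendix 1 schedules an ECG at Visit 2 and none at screening. This document does not place the Visit 2 ECG before dosing.
- *Troponin.* The scheduled test is pre-dose, so a second, post-dose result is needed. Section 3.8.2 lets an unscheduled visit feed the baseline only if it precedes first dosing. The result must therefore sit under the Day 1 visit itself, which is possible because Appendix 1 has standard-of-care results reviewed at Visit 2.

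**Step 4: size per affected subject.** With 60 subjects randomised 1:1, there are 60 / 2 = 30 per arm. One misclassified subject moves 1 / 30 = 3.3 percentage points between cells. The share is larger if fewer than 30 count, since subjects with a missing baseline or post-baseline value leave the denominator in both tables. The number of subjects meeting Step 3 is not in the document and may be zero.

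**The case against.** The strongest reply is that other text already blocks most routes to the error.

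- **Section 3.8.2** keeps post-dose unscheduled visits out of the baseline. This stands for records entered as unscheduled. It does not reach records filed under the Day 1 visit.
- **Standard-of-care tests** are mentioned in 7.5 and 7.6 on the post-baseline side, and neither section says that they feed the baseline. This stands. A reader might infer that any evening standard-of-care test on Day 1 would become the baseline, but the document does not support that.
- **Troponin** is scheduled pre-dose, and its table and listing are numbered among the laboratory outputs, so the date/time limit in 7.2.1 might apply. The first part stands and makes troponin the weaker case. The second is arguable, because 7.2.1 concerns numeric results and 7.6 tabulates troponin as normal or abnormal.
- **The ECG argument rests on silence.** One ECG is scheduled, at a visit labelled as baseline, and the protocol may fix its timing. This is fair. The missing footnote does not show that any ECG was taken post-dose; it shows only that this document does not rule it out.
- **Direction.** A reader might infer that the rule systematically conceals cardiac harm. It does not: subjects A and B err in opposite directions, and the lowest-severity tie rule favours detecting worsening.
- **Consequence.** The tables carry no formal testing. All ECG and troponin results are listed by subject, and the cardiac adverse event summaries do not use this baseline. All of this stands and limits the severity.

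What remains is an inconsistency within the plan. A program written from the categorical sentence would select the on-drug record in the situation of Step 3.

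**Conclusion.** The inconsistency is real, and its severity is minor. The categorical baseline lacks the time limit that the plan applies to same-day continuous repeats, laboratory values and vital signs, and the ECG and troponin tables depend on it. Where several timed records sit under the Day 1 visit and the last is post-dose, the shift is misclassified, in either direction. The risk is mainly for ECG and smaller for troponin.

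Each affected subject moves about 3.3 percentage points if 30 per arm count. The total effect cannot be computed. The conclusion assumes that collection times are recorded and that 7.5 and 7.6 take their baseline from the categorical rule in 3.8.3. The document does not support the inference that a cardiac signal has been or will be lost: it does not show that any subject is affected, and the by-subject listings keep every record.

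**What to change.** - In 3.8.3, change the categorical baseline to the last available record before the date and time of first dose.
- Keep the existing lowest-severity rule for untimed or simultaneous Day 1 records. Falling back to a record before Day 1 would not work for ECG, since none is scheduled then, and subjects would lose their baseline needlessly.
- In 7.5 and 7.6, refer to this rule and say that Day 1 records timed after the first dose count as post-baseline, even when filed under the Day 1 visit.

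The cost is one phrase, two cross-references and a date-time comparison in programming, with no new data collection. The downside is that a subject whose only ECG or troponin on or before Day 1 is timed after dosing will have a missing baseline. That subject leaves the shift-table denominator and, for ECG, the new-abnormality analysis. The number of such subjects is unknown and should be reported beside the tables.

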4. SUBJECT DISPOSITION

4.1. Subject Enrollment and Disposition

A summary of subject enrollment will be provided by treatment group for each country, investigator within a country, and overall. The summary will present the number and percentage of subjects enrolled. For each column, the denominator for the percentage calculation will be the total number of subjects analyzed for that column.

A similar enrollment table will be provided by randomization stratum. The denominator for the percentage of subjects in the stratum will be the total number of randomized subjects. If there are discrepancies in the value used for stratification assignment between the IWRS and the clinical database or other source documents, the value collected in the clinical database will be used for the summary. A listing of subjects with discrepancies in the value used for stratification assignment between the IWRS and the clinical database at the time of data finalization will be provided.

The randomization schedule used for the study will be provided as an appendix to the CSR.

A summary of subject disposition will be provided by treatment group. This summary will present the number of subjects screened, the number of subjects who met all eligibility criteria but were not randomized with reasons subjects not randomized, the number of subjects randomized, and the number of subjects in each of the categories listed below:

- Full Analysis Set
- Safety Analysis Set
- Per-Protocol Analysis Set
- PK Analysis Set
- Completed study drug
- Did not complete study drug with reasons for premature discontinuation of study drug
- Completed study
- Did not complete the study with reasons for premature discontinuation of study
- Completed Extended Viral Load Monitoring Period
- Did not complete the Extended Viral Load Monitoring Period with reasons for premature discontinuation of Extended Viral Load Monitoring Period

For the status of study drug and study completion and reasons for premature discontinuation, the number and percentage of subjects in each category will be provided. The denominator for the percentage calculation will be the total number of subjects in the Safety Analysis Set corresponding to that column.

The following by-subject listings will be provided by subject identification (ID) number in ascending order to support the above summary tables:

- Reasons for premature study drug or study discontinuation
- Reasons for screen failure (will be provided by screening ID number in ascending order)

4.2. Extent of Study Drug Exposure and Adherence

Extent of exposure to study drug will be examined by assessing the total duration of exposure to study drug and the level of adherence to the study drug specified in the protocol.

4.2.1. Duration of Exposure to Study Drug

Total duration of exposure to study drug will be defined as last dosing date minus first dosing date plus 4, regardless of any temporary interruptions in study drug administration, and will be expressed in days using up to 1 decimal place (eg, 4.5 days). If the last study drug dosing date is missing, the latest date among the study drug end date, clinical visit date, laboratory sample collection date, and vital signs assessment date that occurred during the on-treatment period will be used.

The total duration of exposure to study drug will be summarized using descriptive statistics (n, mean, SD, median, Q1, Q3, minimum, and maximum), and using the number and percentage of subjects exposed through the following time periods: Day 1 (Baseline), Day 5, Day 9, Day 13, and Day 17. Summaries will be provided by treatment group for the Safety Analysis Set.

No formal statistical testing is planned.

4.2.2. Adherence to Study Drug

The total number of tablets administered will be summarized using descriptive statistics.

The presumed total number of tablets administered to a subject will be determined by the data collected on the drug accountability eCRF using the following formula:

$$\begin{aligned} & \text{Total Number of Tablets Administered} \\ &= \left(\sum \text{No. of Tablets Dispensed at Study Dosing Visits} \right) \end{aligned}$$

The level of prescribed adherence to the study drug regimen will be determined by the total amount of study drug administered relative to the total amount of study drug specified by the protocol for a subject who completes treatment in the study.

The level of prescribed adherence will be expressed as a percentage using the following formula:

$$\text{Prescribed Adherence (\%)} = \left(\frac{\text{Total Amount of Study Drug Administered}}{\text{Total Amount of Study Drug Specified by Protocol}} \right) \times 100$$

Descriptive statistics for adherence (sample size, mean, SD, median, Q1, Q3, minimum, and maximum) along with the number and percentage of subjects belonging to adherence categories (eg, < 80% and $\geq 80\%$) will be provided by treatment group for the Safety Analysis Set.

No formal statistical testing is planned.

A by-subject listing of study drug administration and drug accountability will be provided separately by subject ID number (in ascending order) and visit (in chronological order).

4.3. Protocol Deviations

Subjects who did not meet the eligibility criteria for study entry, but enrolled in the study will be summarized regardless of whether they were exempted by the sponsor or not. The summary will present the number and percentage of subjects who did not meet at least 1 eligibility criterion and the number of subjects who did not meet specific entry criteria by treatment group based on the All Randomized Analysis Set. A by-subject listing will be provided for those subjects who did not meet at least 1 eligibility (inclusion or exclusion) criterion. The listing will present the eligibility criterion (or criteria if more than 1 deviation) that subjects did not meet and related comments, if collected.

Protocol deviations occurring after subjects entered the study are documented during routine monitoring. The number and percentage of subjects with important protocol deviations by deviation reason (eg, nonadherence to study drug, violation of selected inclusion/exclusion criteria) will be summarized by treatment group for All Randomized Analysis Set. A by-subject listing will be provided for those subjects with any protocol deviation.

5. BASELINE CHARACTERISTICS

5.1. Demographics

Subject demographic variables (ie, age, sex, race, and ethnicity) will be summarized by treatment group and overall using descriptive statistics for age, and using number and percentage of subjects for sex, race, and ethnicity. The summary of demographic data will be provided for the Safety Analysis Set.

In addition, a similar summary table will be provided by the consent status of participation in the Extended Viral Load Monitoring (yes or no).

A by-subject demographic listing, including the informed consent date, will be provided by subject ID number in ascending order.

5.2. Other Baseline Characteristics

Other baseline characteristics include:

- Weight (kg)
- Height (cm)
- Body mass index (BMI; in kg/m²)
- RSV types (RSV A or RSV B)
- Vital signs (pulse rate, systolic and diastolic blood pressure, body temperature, and respiratory rate)
- Smoking history
- Viral load
- Detectable RSV in nasal swab samples
- Co-pathogen types
- Duration of respiratory symptoms prior to the first dosing date
- Stratification factors
- Hospitalization (including hospitalization on the date of the first study drug administration Yes/No, hospitalized types, duration of hospitalization prior to the date of the first study drug administration, hospitalization reasons, hospitalization related to RSV infection)

These baseline characteristics will be summarized by treatment groups and overall using descriptive statistics (n, mean, SD, median, Q1, Q3, minimum, and maximum) for continuous variables and using number and percentage of subjects for categorical variables. In addition, baseline characteristics will be summarized by the consent status of participation in the Extended Viral Load Monitoring (yes or no) in a separate table. The summary of baseline characteristics will be provided for the Safety Analysis Set. No formal statistical testing is planned.

A by-subject listing of the baseline characteristics will be provided by subject ID number in ascending order.

